**Release date:8-5-2025**

# **EFFICACY OF INPATIENT PULMONARY REHABILITATION PROGRAM IN ELDERLY PATIENTS WITH ACUTE EXACERBATION OF COPD: A RANDOMIZED CONTROL TRIAL.**

## **Introduction**

Chronic Obstructive Pulmonary Disease (COPD) is now one of the top three causes of death worldwide, and 90% of these deaths occur in low- and middle-income countries (LMICs) [1, 2]. Previous studies illustrated that older adults with COPD have a high risk of experiencing AECOPD, which typically leads to decreased lung function, an increased incidence of respiratory failure, and even death [3]. Acute exacerbation (AE) of COPD (AECOPD) is defined as episodes of acute worsening of respiratory symptoms (such as dyspnea, coughing, and sputum production) that require additional therapy [4]. AECOPD is responsible for patients' clinical deterioration.

Patients requiring hospitalisation are associated with poor outcomes, including accelerated declines in muscle strength and lung function, a reduced health status and quality of life (QOL), accelerated disease progression, a significant risk of recurrent exacerbation, and an increased risk of mortality [5]. Increase population ageing, in addition to a large percentage of elderly experiencing AECOP, will lead to extra efforts in healthcare systems, in addition to high costs of medical care services. Seeking cost-effective ways is the aim of international societies concerning COPD.

The study aimed to identify the effect of early pulmonary rehabilitation in elderly patients with Acute exacerbation (AE) of COPD (AECOPD) on exercise tolerance, dyspnea, sleep quality, fatigue, and time from hospital admission till discharge from the hospital.

## **Methods**

### **Participants**

A prospective, supervised, blinded randomised controlled trial (RCT) will be conducted at Alzahraa University Hospital, in the inpatient department of Chest disease, Cairo, Egypt. Participants were allocated to the two groups using computer-generated random allocation sequences. The codes were determined by using serially numbered block sizes will be kept in sealed and opaque envelopes in a locked office. Participants' healthcare providers were blinded to the group assignment.

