### **Fatigue Severity Scale (FSS)**

The Fatigue Severity Scale (FSS) is a nine-item self-administered questionnaire. Each item is scored between 1 and 7, and a lower total score indicates a decrease in fatigue [9].

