## **Exercise Program**

**Group A: They will** Perform a physical therapy program that will be completed two daily sessions till discharge from the hospital, starting from randomization until hospital discharge. Administered twice per day, seven times per week,

**Group B:** A control group will only receive medical treatment from hospital admission until discharge.

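### The unqualified claim that healthcare providers are blinded cannot hold for the staff who give the sessions and has no stated support for the ward team

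*Protocol*

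**What the plan says.** The Participants section describes the design as "A prospective, supervised, blinded randomised controlled trial (RCT) will be conducted at Alzahraa University Hospital" and places it "in the inpatient department of Chest disease, Cairo, Egypt". It names one blinded party, the participants' own providers: "healthcare providers were blinded to the group assignment". No role is excepted.

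The Exercise Program section has Group A "Perform a physical therapy program that will be completed two daily sessions till discharge from the hospital", starting at randomization, and fixes the frequency: "Administered twice per day, seven times per week". For the other arm it says: "A control group will only receive medical treatment from hospital admission until discharge".

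The study aim in the Introduction lists five outcomes: exercise tolerance, dyspnea, sleep quality, fatigue and "time from hospital admission till discharge from the hospital". The fatigue scale is described as a "nine-item self-administered questionnaire".

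**The concern.** The blinding statement and the description of the arms do not fit together. One arm has frequent, physical, supervised contact throughout the stay, and the other has none. People who deliver that contact are healthcare providers and cannot be unaware of the group. People who look after the same inpatients can probably tell who is having sessions.

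The outcome most exposed is time to discharge. Where the treating team decides when a patient leaves, a team that knows the group may release Group A sooner because those patients seem fitter, or later so that sessions can continue. Either would move the difference in stay without any effect of the exercise. A reader who trusts the blinding statement would discount that possibility when the protocol gives no ground for doing so.

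Fatigue is a different case. It is completed by the patient, so provider blinding would not protect it even if it were achieved.

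**Working it through.** The point is one of consistency, and the protocol states no figure to reproduce. The steps are as follows.

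1. **Scope of the claim.** The Participants section covers participants' healthcare providers as a class. It does not separate therapists, ward physicians, nurses or outcome assessors.

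2. **Contrast between the arms.** Reading the frequency as two sessions on each of seven days, Group A has 2 × 7 = 14 sessions per patient-week. Group B has 0. The word *only* in the Group B sentence rules out a sham or attention contact.

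3. **Staff who give sessions.** They know the group of every patient they treat. For them the claim is false.

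4. **Ward staff.** Both groups are inpatients of one chest department. The protocol describes no separate location, no separate notes and no other means of hiding the sessions. Awareness is likely but not proved, so here the claim is unsupported rather than disproved.

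5. **Envelopes.** The sealed opaque envelopes in the Participants section conceal the sequence before assignment. They do nothing to keep staff unaware afterwards.

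6. **Link to an outcome.** Time to discharge depends on a decision. The protocol does not say who takes it or on what criteria. If the treating team does, steps 3 and 4 mean that the outcome cannot be called provider-blinded.

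**Illustration only.** To show how a shift caused by knowledge of the group would act, suppose that exercise has no true effect and that stay is compared by a two-sided 5% two-sample t-test with n per group. The rejection rate comes from the noncentral t distribution with df = 2n − 2 and noncentrality (shift/SD) × √(n/2). The shift, the SD, n and the test itself are all assumptions. The protocol gives none of them, and its Sample size calculation section states no number.

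| n per group | SD (days) | df | Noncentrality, 0.5-day shift | Rejection rate | Noncentrality, 1-day shift | Rejection rate |
|---|---|---|---|---|---|---|
| 20 | 5 | 38 | 0.1 × √10 = 0.316 | 6.1% | 0.2 × √10 = 0.632 | 9.5% |
| 30 | 3 | 58 | 0.167 × √15 = 0.645 | 9.7% | 0.333 × √15 = 1.291 | 24.6% |
| 40 | 2 | 78 | 0.25 × √20 = 1.118 | 19.7% | 0.5 × √20 = 2.236 | 59.8% |

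With no shift the rate is 5.0% in every row. The table shows how sensitive the result would be to such a shift. It does not show that a shift occurs in this trial.

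**The case against.** The best defence is that the sentence was meant for the medical team on the ward, as distinct from trial therapists. The protocol does not say where sessions take place, who gives them, or whether the discharging physician sees them or the therapy notes. The Group A text also ends on a comma and may have lost words. The lack of a sham unblinds patients and therapists for certain, but does not prove that every discharging physician knows the group.

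Much of this stands, and it limits the point. A reader might infer that the protocol claims blinding for time to discharge in particular. It does not: it makes one general statement about providers, and the link to discharge rests on how discharge is usually decided. A reader might also infer that ward staff certainly know the group, or that the stay result is shown to be biased. The protocol says neither that sessions are in view nor who decides discharge. The percentages above cannot close that gap, since any endpoint given an artificial shift would show the same pattern, and a span of 6.1% to 59.8% says little about this trial.

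What does not stand is the rescue of the sentence itself. It makes no distinction between roles and is backed by no procedure. The Group B sentence is complete, so lost Group A text could not supply a sham. Even on the kindest reading, the wording needs correcting.

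It may also be tempting to replace actual discharge by a discharge-readiness endpoint rated daily by an outside assessor. That goes too far. It needs extra staff, and it changes what the trial sets out to measure, when the Introduction's concern with the cost of care fits actual stay. Without a rule for patients discharged before the criteria are met, it would let the ward team's decision back in.

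**Conclusion.** The concern holds in a limited form. The provider-blinding statement is wrong for staff who give sessions, and for ward staff it is doubtful and supported by no stated procedure. That follows from the text alone and needs no assumption.

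The consequence for time to discharge rests on one assumption, that the treating team decides discharge. This is usual but not stated. On that assumption the stay result cannot be presented as provider-blinded. The only measure of size taken from the document is the contrast of 14 sessions per patient-week against 0. The amount and direction of any bias are unknown, and the rejection rates carry no weight in this conclusion.

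This should be corrected because it is a false statement about a property of the design, it bears on a listed outcome, and the correction is cheap. It does not call the trial into question.

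**What to change.** In the Participants section, replace the sentence on provider blinding with: *Patients and the therapists who give sessions are not blinded, and blinding of the ward team is not claimed because Group B has no sham.*

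Keep actual time to discharge as the outcome. Have the existing team apply one written list of discharge criteria, fixed before the first enrolment, to both groups alike. Report the stay result as decided by a team not blinded to group.

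The corrected sentence costs nothing. The criteria need one list to be written and followed by staff already in place, and neither arm's treatment changes. The downside is that the trial can no longer call itself provider-blinded. Common criteria narrow the room for judgement about discharge but do not remove it, so some bias in stay may remain.

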### **Sample size calculation.**

Before the participants were included in the study, the sample size was measured using Epi Info™ program version 7. 2. Based on the previous study [6].

### **Inclusion criteria**

Patients with mild to moderate acute exacerbation of COPD in both genders 2) were older than 65 years, 3) were in clear consciousness, 4) had been diagnosed with shortness of breath or dyspnea that was not caused by heart disease, pneumothorax, or pulmonary oedema

**Exclusion criteria** were 1) systolic blood pressure lower than 90 mmHg, 2) an unstable psychological status, hemoptysis, pneumothorax, pulmonary oedema, and the use of a respirator

### **Ethical considerations**

The study was approved by the ethical committee of the Faculty of Medicine for Girls- Al-Azhar University, Cairo, Egypt, number (2723). The principal investigator explained to the patients the objectives, the implementation process,

Inclusion criteria, and exclusion criteria of the study. In addition, the patients were informed that they could withdraw from the study at any time if they felt unwell, and they were enrolled only after signing informed consent forms

## **Assessment**

### **Diagnosis of COPD**

The presence of non-fully reversible airflow obstruction ( $FEV1/FVC < 0.7$  post-bronchodilation) measured by spirometry confirms the diagnosis of COPD [7]. The patients were admitted to the hospital for over 24 hours and diagnosed with COPD based on the Global Initiative for Obstructive Lung Disease guideline. The presence of non-fully reversible airflow obstruction ( $FEV1/FVC < 0.7$  post-bronchodilation) measured by spirometry confirms the diagnosis of COPD [7]. Patients medically controlled by medication recommended by GOLD2024.

The diagnostic approach to AECOPD is confirmed based on the clinical setting and severity of the exacerbation. After history and examinations, including oximetry, sputum culture, chest X-ray [8].

### **Fatigue Severity Scale (FSS)**

The Fatigue Severity Scale (FSS) is a nine-item self-administered questionnaire. Each item is scored between 1 and 7, and a lower total score indicates a decrease in fatigue [9].

## **Exercise Program**

**Group A: They will** Perform a physical therapy program that will be completed two daily sessions till discharge from the hospital, starting from randomization until hospital discharge. Administered twice per day, seven times per week,

**Group B:** A control group will only receive medical treatment from hospital admission until discharge.

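### Does the silence on when fatigue, dyspnea, sleep quality and exercise tolerance are measured spoil the comparison of the arms?

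*Protocol*

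**What the plan says.** The aim, in the Introduction, is to find the effect of early rehabilitation "on exercise tolerance, dyspnea, sleep quality, fatigue, and time from hospital admission till discharge from the hospital". Length of stay is therefore one of five outcomes.

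Under Assessment, the diagnosis text contains one time reference, "The patients were admitted to the hospital for over 24 hours", which concerns admission and diagnosis. The only outcome instrument described there is the Fatigue Severity Scale, a "nine-item self-administered questionnaire". Its scoring is given ("Each item is scored between 1 and 7, and a lower total score indicates a decrease in fatigue"), but not the time at which it is completed.

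Under Exercise Program, Group A's sessions run "starting from randomization until hospital discharge". For the other arm the text is: "A control group will only receive medical treatment from hospital admission until discharge". These sentences describe treatment periods. Nowhere is a baseline or follow-up assessment time stated for the four outcomes other than length of stay.

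**The concern.** An assessment schedule is a data-collection rule. It normally stands in the protocol, and no analysis plan can recover values that were never collected, so an unseen SAP does not answer the point.

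The only end named for either arm is discharge, and the programme may bring discharge forward or push it back. If stays differ by arm and the outcomes are taken only at discharge, patients are compared after different lengths of time. Discharge is also likely to be granted when a patient has recovered enough, which pulls the arms together at that moment. A programme that works by speeding recovery could then show little difference in fatigue or dyspnea. A programme that lengthened stay could look better than it is. The start points are worded differently too: Group A's sessions from randomisation, Group B's treatment from admission.

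At stake is whether the symptom comparison may be read as an effect at equal time after randomisation.

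**Working it through.** **What the text establishes.** The aim lists the outcomes without times. The Assessment section gives diagnosis and scoring without times. The Exercise Program section gives treatment periods that end at discharge. Set side by side, these show silence on timing. They do not show an instruction to measure at discharge, nor one to measure the arms at different times.

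**Size of the possible distortion.** The protocol has no figure to reproduce. The only usable input is the range of the fatigue total: nine items scored 1 to 7 give 9 × 1 = 9 to 9 × 7 = 63. Everything below is assumed.

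*Simple shift.* Suppose patients improve by *s* points a day, stays differ by *d* days, and stay is unrelated to the score. Measuring at discharge then shifts the difference between arms by about *s* × *d*. With *s* = 0.5 to 2 and *d* = 1 to 3, this is 0.5 × 1 = 0.5 up to 2 × 3 = 6 points. With *d* = 0 it is nil.

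*Discharge driven by the score.* The simulation has 200,000 patients per arm and a baseline total N(45, 8). The daily fall is N(1.5, 0.5), floored at 0.3, plus 0.4 in Group A while in hospital. Discharge is on the first day from 2 to 21 when score plus noise (SD 4) is 35 or less. Variant 2 uses a daily fall of 2.0 and an extra 0.5. Differences are A minus B.

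| | Variant 1 | Variant 2 |
|---|---|---|
| Mean stay, B v A (days) | 6.98 v 5.82 | 5.59 v 4.70 |
| Fatigue difference at discharge | −0.82 | −0.77 |
| Day 3 | −1.08 | −1.36 |
| Day 5 | −1.54 | −1.85 |
| Standardised, unadjusted: discharge / day 3 | 0.143 / 0.119 | 0.134 / 0.148 |
| Standardised, baseline-adjusted: discharge / day 3 | 0.157 / 0.196 | 0.146 / 0.241 |

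The gain in visible effect from a fixed day over discharge is:
- Day 3: 1.08 − 0.82 = 0.26 and 1.36 − 0.77 = 0.59 points.
- Day 5: 1.54 − 0.82 = 0.72 and 1.85 − 0.77 = 1.08 points.

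The faster recovery does not vanish in the discharge comparison. It reappears as a shorter stay, by 6.98 − 5.82 = 1.16 and 5.59 − 4.70 = 0.89 days, and length of stay is already an outcome.

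**Cost of a fixed day.** Some patients would be home and would have to be telephoned for a self-administered scale. Mode distortion = shift from telephoning × difference between arms in the share at home. Take an assumed shift of 1 to 3 points.

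- Score-driven discharge, day 3: shares at home 21.8% (B) v 24.5% (A), and 25.4% v 29.0%. Distortion is 1 × 0.027 = 0.03 to 3 × 0.036 = 0.11 points.
- Score-driven discharge, day 5: 41.6% v 47.6%, and 49.0% v 57.0%. Distortion is 1 × 0.060 = 0.06 to 3 × 0.080 = 0.24 points.
- Stay unrelated to score, N(7.5, 2.5) in B and 1.6 days shorter in A. Day 3: Φ(−1.80) = 3.6% v Φ(−1.16) = 12.3%. Day 5: Φ(−1.00) = 15.9% v Φ(−0.36) = 35.9%. The upper distortion is 3 × 0.087 = 0.26 points on day 3 and 3 × 0.200 = 0.60 on day 5.

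At its upper end the distortion is of the same order as the gain.

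**The case for a change.** The strongest case for a change is that the text as it stands permits any assessment time, even different times in the two arms, and that one sentence would close the gap. The questionnaire is short, discharge values could be kept, and data not collected cannot be recovered later. The illustration gives some support. With baseline adjustment the standardised difference is larger on day 3 than at discharge in both variants, and larger still on day 5 (0.270 and 0.314). If discharge is modelled in continuous time, the difference at discharge falls to 0.47 and 0.30 points. Under score-driven discharge the mode distortion is also clearly smaller than the gain.

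The factual part stands: no time is given, and writing one down would make the protocol clearer. The rest does not carry a required change.

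- Nothing in the aim says that an equal-time effect is the intended question. A programme defined as running to discharge can properly be judged by status at discharge, with length of stay beside it.
- The size depends wholly on assumptions. The two models above give anything from tenths of a point to 6 points, and no input beyond the scale range comes from the protocol.
- Exercise tolerance could be tested on a fixed day only in patients still in hospital. They are a group selected after randomisation, possibly differently by arm.
- The different start points do not bias the comparison in themselves. Randomisation takes place in hospital, and a baseline at entry to the trial is the ordinary choice in both arms.

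**Conclusion.** No change to the plan is called for. The protocol is silent on assessment times; it does not fix a wrong one. A trial team would ordinarily fill this gap by measuring at entry and at discharge and reporting the result beside length of stay. That yields a sound conclusion, provided it is read as status at discharge and not as the effect at equal time after randomisation. Adding a common early day is a trade-off: an assumed gain of about 0.3 to 0.6 points on day 3 or 0.7 to 1.1 on day 5, against an assumed mode distortion of up to about 0.3 or 0.6 points, extra calls, missing values, and no full remedy for exercise tolerance.

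This rests on two assumptions: that both arms are assessed at the same milestones, and that stays do not differ so much that status at discharge ceases to be informative. All the simulated figures are illustrations and are not evidence of size in this trial. The protocol text states no sample size, so the effect on power cannot be checked.
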